#### ***4.1 Informed Consent Process***

Potential eligible patients will be confirmed with both the most responsible physician (MRP) and the site investigator within the first 5 days (i.e. 120 hours) of hospital admission. Eligible patients will be consented by a research coordinator or health care worker (other than the MRP) within the first 5 days (i.e. 120 hours) of hospital admission using remote methods (such as telephone consent or eConsent) to obtain verbal or written consent to minimize the risk of COVID-19 exposure, conserve the use of personal protective equipment and prevent COVID-19 research document contamination. Informed consent is to be obtained directly from the patient or from their legally authorized substitute decision maker (applies to initial consent and ongoing consent, should the participant lose capacity during the trial). Capacity will be assessed by the circle of care. Also, where possible, to minimize the burden to the patient, patients may be consented to more than one COVID-19-related clinical trial at a time.

We will follow Health Canada's Management of clinical trials during the COVID-19 pandemic: Notice to Clinical Trial Sponsors.

#### ***4.2 Treatment Allocation***

PI/Co-I will determine eligibility prior to notifying the research coordinator by phone and email to begin randomization process. Central randomization will occur using an interactive web response system. This is an open label study thus once a participant is randomized, a research coordinator will document the treatment allocation in the case report form and notify the MRP and study team by email and phone of the patient's study treatment allocation (therapeutic or standard care arm). The MRP will then order the study drug in the patient's medical chart and notify the study team. The research coordinator will then email or fax research pharmacy the order. Research pharmacy will follow their SOP to dispense study drug and study drug will be dispensed via research pharmacy to the treating medical team.

### **5.0 Description of Treatment vs. Standard Care**

#### ***5.1 Therapeutic Anticoagulation***

Therapeutic anticoagulation with LMWH or UFH (high dose nomogram). The choice of LMWH versus UFH will be at the clinician's discretion and dependent on local institutional supply. LMWH options are described in Table 1 (18–20). UFH will be administered using a weight-based nomogram (bolus plus continuous infusion) with activated partial thromboplastin time (aPTT) or UFH anti-Xa titration according to the center-specific institutional protocols as per venous thromboembolism treatment (i.e. high dose nomogram). UFH anti-Xa titration is preferred over aPTT if available as achieving a therapeutic aPTT may be challenging in patients with a pro-inflammatory state such as COVID-19. Therapeutic anticoagulation will be administered until hospital discharge, death or day 28. If the patient is admitted to the ICU or requiring ventilatory support (i.e. patient reaches a component of the primary outcome), we recommend continuation of the allocated treatment as long as the treating physician is in agreement.

**Table 1. Therapeutic Dose Anticoagulation**

Any of the following strategies may be used for high-dose anticoagulation:

CrCl	BMI	Enoxaparin	Dalteparin	Tinzaparin	UFH	
$\geq 30$	<40	1 mg/kg SC q12h OR 1.5 SC mg/kg q24h	200 units/kg SC q24h OR 100 IU/kg SC q12h	175 U/kg SC q24h	IV bolus, with continuous infusion to titrate to institution specific anti-Xa or aPTT values*	
	$\geq 40$	1 mg/kg q12h &	100 units/kg SC q12h &	175 U/kg SC daily &		
$<30$	<40	UFH IV bolus, with continuous infusion to titrate to institution specific anti-Xa or aPTT values* or LMWH per hospital protocol taking BMI into consideration as above				
	$\geq 40$					

Abbreviations: CrCl = creatinine clearance; BMI = body mass index; \* Initial bolus dose determined by sites, encouraging use of dosing algorithm designed for treatment of VTE. UFH anti-Xa titration is preferred over aPTT if available as achieving a therapeutic aPTT may be challenging in patients with a pro-inflammatory state such as COVID-19.

&For patients with BMI above 40, measurement of anti-Xa to confirm therapeutic effect can be used.

Table 2 outlines the investigational products chosen for this study, mechanism of action and rationale for use.

**Table 2. Investigational Products Rationale for Inclusion**

Drug	Mechanism of Action	Route	Rationale for Inclusion
Unfractionated heparin	Indirect anticoagulant that forms a complex with antithrombin enhancing the inhibition of several activated blood coagulation factors: thrombin (factor IIa), factor IXa, Xa, XIa and XIIa.	Intravenous (IV) Subcutaneous (SC)	Considered standard care for both prophylactic and therapeutic dose anticoagulation for acutely ill hospitalized medical patients therefore, included as an option in both the standard care (control) arm and therapeutic anticoagulation (experimental) arm.
Dalteparin	Indirect anticoagulant that forms a complex with antithrombin enhancing the inhibition of coagulation factor Xa and thrombin (factor IIa).	SC	Considered standard care for both prophylactic and therapeutic dose anticoagulation for acutely ill hospitalized medical patients therefore, included as an option in both the standard care (control) arm and therapeutic anticoagulation (experimental) arm.
Enoxaparin	Indirect anticoagulant that forms a complex with antithrombin enhancing the inhibition of coagulation factor Xa and thrombin (factor IIa).	SC	Considered standard care for both prophylactic and therapeutic dose anticoagulation for acutely ill hospitalized medical patients therefore, included as an

			option in both the standard care (control) arm and therapeutic anticoagulation (experimental) arm.
Tinzaparin	Indirect anticoagulant that forms a complex with antithrombin enhancing the inhibition of coagulation factor Xa and thrombin (factor IIa).	SC	Considered standard care for both prophylactic and therapeutic dose anticoagulation for acutely ill hospitalized medical patients therefore, included as an option in both the standard care (control) arm and therapeutic anticoagulation (experimental) arm.
Fondaparinux	Indirect anticoagulant that forms a complex with antithrombin enhancing the inhibition of coagulation factor Xa.	SC	Considered standard care for prophylactic dose anticoagulation for acutely ill hospitalized medical patients therefore, included as an option in the standard care (control) arm but not in the therapeutic anticoagulation (experimental) arm.

## 5.2 Standard Care

In Canada and the US, administration of LMWH, UFH or fondaparinux at thromboprophylactic doses for acutely ill hospitalized medical patients, in the absence of contraindication, is generally considered standard care. Importantly, the doses of thromboprophylaxis only include those listed below (Table 3) given the current equipoise surrounding the effectiveness of weight-based dose adjusted thromboprophylaxis in acutely ill medical inpatients.

Descriptions of the Investigational Products and Standard Care are provided in Table 3 below.

**Table 3. Standard care (low dose, prophylactic) anticoagulation**

Any of the following strategies may be used for low-dose anticoagulation (doses above those listed would not be considered as low dose {prophylactic}. A patient is receiving a lower dose of either LMWH or UFH than listed below, due to extremely low weight/BMI, would still be acceptable and considered as part of standard care {low dose, prophylactic anticoagulation}):

**Prophylactic Dose Anticoagulation**

CrCl	BMI	Enoxaparin	Dalteparin	Tinzaparin	Fondaparinux	Unfractionated Heparin (UFH)
$\geq 30$	<40	40 mg SC q24h	5000 units SC q24h	4500 U SC q24h	2.5 mg SC q24h	5000 units SC q8-12h
	$\geq 40$	40 mg SC q12h	5000 units SC q12h	9000 (+/- 1000) U SC q24h	not applicable	7500 units SC q8h
<30	<40	UFH 5000 units SC q8-12h or LMWH per hospital protocol taking BMI into consideration as above				
	$\geq 40$	UFH 7500 units SC q8h or LMWH per hospital protocol taking BMI into consideration as above				

Abbreviations: CrCl = creatinine clearance; BMI = body mass index

Type and doses of thromboprophylactic LMWH or UFH will be recorded in the case report forms. Concomitant medications and co-enrollment of other COVID-19 trials will also be recorded.

Full therapeutic dose anticoagulation (therapeutic dose UFH or LMWH) is permitted as rescue therapy in the event of suspected or confirmed thromboembolism. Additional rescue therapy, in the form of thrombolysis (with tissue plasminogen activator), is also permitted if deemed clinically warranted by the treating clinical team.

Institutional drug stock will be used, and the institutional pharmacy will be responsible for labelling and distribution. No repackaging of drugs will occur.

**Table 4. Formulations of Investigational Products and Standard Care**

Common Name	Brand Name	Formulation	Manufacturer	DIN(s)
Tinzaparin Sodium	Innohep	10000 Unit / mL, 20000 Unit / mL, 8000 Unit / 0.4 mL, 12000 Unit / 0.6 mL, 16000 Unit / 0.8 mL	Leo Pharma Inc.	02167840, 02229515, 02229755, 02231478, 02358158, 02358166, 02358174, 02358182, 02429462, 02429470, 02429489
Enoxaparin Sodium	Lovenox	30 mg / 0.3 mL, 40 mg / 0.4 mL, 60 mg / 0.6 mL, 80 mg / 0.8 mL, 100 mg / mL	Sanofi-Aventis Canada Inc.	02012472, 02236883, 02378426, 02378434, 02378442
Enoxaparin Sodium	Lovenox HP	120 mg / 0.8 mL, 150 mg / mL	Sanofi-Aventis Canada Inc.	02242692, 02378469
Enoxaparin Sodium	Lovenox With Preservative 300mg/3mL	100 mg / mL	Sanofi-Aventis Canada Inc.	02236564
Dalteparin Sodium	Fragmin	2500 Unit / 0.2 mL, 5000 Unit / 0.2 mL, 10000 Unit / mL, 25000 Unit / mL, 7500 Unit / 0.3 mL, 10000 Unit / 0.4 mL, 12500 Unit / 0.5 mL, 15000 Unit / 0.6 mL, 18000 Unit / 0.72 mL, 3500 Unit / 0.28 mL	Pfizer Canada Inc.	02132621, 02132648, 02132664, 02231171, 02352648, 02352656, 02352664, 02352672, 02352680, 02430789
Heparin Sodium	Heparin Leo	100 Unit / mL,	Leo Pharma Inc.	0727520, 00453811

		1000 Unit / mL		
Heparin Sodium	Heparin Sodium Injection, USP	1000 Unit / mL, 10000 Unit / mL,	Fresenius Kabi Canada Ltd.	02264307, 02264315, 02392453
Heparin Sodium	Heparin Sodium Injection USP	1000 Unit / mL, 10000 Unit / mL	Sandoz Canada Inc.	02303086, 02303108, 02303094
Heparin Sodium	Heparin Sodium Injection USP	5000 Unit / 0.5 mL	Sterinova Inc.	02456958
Heparin Sodium	Heparin Sodium Injection USP	10000 Unit / ML	Pfizer Canada Inc.	02382326
Heparin Sodium	Heparin Sodium In 0.9% Sodium Chloride Injection	2 Unit / mL	Pfizer Canada Inc.	01990748
Heparin Sodium	Heparin Sodium And 0.9% Sodium Chloride Injection	2 Unit / mL	Baxter Corporation	00828750
Heparin Sodium	Heparin Sodium 25000 Units In 5% Dextrose Injection	10000 Unit / 100 mL	B. Braun Medical Inc.	02209721
Heparin Sodium	Heparin Sodium 20000 Units In 5% Dextrose Injection	4000 Unit / 100 mL	B. Braun Medical Inc.	02209713
Heparin Sodium	Heparin Sodium In 5% Dextrose Injection, 25000 Unit/500mL	5000 Unit / 100 mL	B. Braun Medical Inc.	01935941
Fondaparinux Sodium	Arixtra	2.5 mg / 0.5 mL, 7.5 mg / 0.6 mL,	Aspen Pharmacare Canada Inc.	02245531, 02258056
Fondaparinux Sodium	Fondaparinux Sodium Injection	2.5 mg / 0.5 mL, 7.5 mg / 0.6 mL	[name] Ltd.	02406853, 02406896

## 6.0 Study Procedures and Evaluations

Please refer to Table 5 for Schedule of Events.

### 6.1 Bloodwork

No study specific bloodwork will be ordered aside from a single D-dimer test (if not collected through standard of care) up to and including day 3 after randomization for all participants in both study arms. In those on the active treatment arm who are receiving UFH, the aPTT or UFH anti-Xa will be drawn according to local institutional UFH nomogram protocol guidance. Where possible, any study specific blood work will be timed along with regularly scheduled clinical blood work to minimize exposure and use of personal protective equipment. All laboratory results (see Table 5 for Schedule of Events) will be collected from standard of care from admission to hospital discharge, death or 28 days, where available. Laboratory parameters of interest include complete blood count (CBC), PT, aPTT or anti-Xa for UFH (according to local institutional protocol), anti-Xa for LMWH, fibrinogen, blood group, ferritin, lactate dehydrogenase (LDH), troponin, C-reactive protein (CRP), creatinine, alanine aminotransferase [ALT], heparin-platelet factor 4 immunoassay.

Details regarding institutional-specific D-dimer coagulation instrumentation and assay, as well as local reference intervals, including units of measure, will be collected from each site.

### 6.2 Optional Biobanking

For hospital sites with capable infrastructure, the study team will collect samples for biobanking of plasma and serum to evaluate the pathophysiologic mechanism of COVID-19 coagulopathy, an entity which is poorly understood, the impact of anticoagulation on biomarkers, and role of biomarkers in predicting outcomes. Samples will be used for future measurement of biomarkers of coagulation, inflammation, endothelial activation or other relevant measures important in COVID-19. Informed consent for the biobanking component will be conducted, where applicable. Blood will be collected three times:

- Day 1 (day of randomization, prior to treatment initiation whenever possible): One serum (5 ml), one EDTA plasma (10 ml), and two 4.5 ml citrate (9 ml) tubes. Total blood volume 24 ml (or closest volume according to blood draw tube size availability at sites)
- Day 3 (at 48h +/- 24h) of randomization: One serum (5 ml), one EDTA plasma (4 ml), and one citrate (4.5 ml) tubes. Total blood volume 13.5 ml (or closest volume according to blood draw tube size availability at sites)
- One of, (1) Day 14 or if any of the following occur earlier: (2) day of discharge; or (3) day of removal from study; or (4) day that the patient reaches a component of the primary outcome (i.e. ICU admission, non-invasive/invasive mechanical ventilation). All drawn +/-24 hours around each time. Repeat Day 3 collection of one serum (5 ml), one EDTA plasma (4 ml), and one citrate (4.5 ml) tubes. Total blood volume 13.5 ml (or closest volume according to blood draw tube size availability at sites)

If the time window for blood collection is problematic due to logistical considerations, collection of the sample as close as possible (before or after) to the target time window is suggested. Phlebotomy will be

timed along with regularly scheduled clinical blood work to minimize exposure and use of personal protective equipment.

Processing and storage of blood samples will follow a simple protocol to aliquot serum, two types of plasma and the cell layer from the EDTA tube will be aliquoted into 6 storage vials. Cryovials and labels will be provided to participating sites by the central biorepository site (see below).

The aliquoted samples will be stored in freezers (at -80°C or colder) in a secure location at the local institution until the COVID-19 pandemic allows for shipping to the central biorepository, the Laboratory for Clinical Biochemistry Research at the University of Vermont ([name]). [name] laboratory will be the custodian of the specimens.

The collection, processing and storage of samples will be outlined in Standard Operating Procedures to ensure consistency in specimen handling and therefore, optimization of their quality. Samples will be used for future measurement of biomarkers of coagulation, inflammation and endothelial activation. The Co-PIs and investigator team will establish a committee to review and approve requests for samples, following procedures established for multi-center research over the past 30 years in [name] laboratory.

We anticipate use of the samples until they are exhausted, but if all scientific use is completed, samples will be destroyed as per institutional practices, at the discretion of the investigator team. All participants will provide informed consent in accord with established procedures, but if they desire withdrawal of their specimens that can be done. Laboratory staff will have no information on participant identity, other personal health information, or randomized treatment assignment.

### ***6.3 Endpoint Assessment***

**Primary outcome (primary endpoint):** The primary composite outcome of ICU admission, non-invasive positive pressure ventilation, invasive mechanical ventilation or death at 28 days.

If a patient is discharged alive before 28 days, vital status will be determined using a telephone follow-up. If a patient was discharged alive on mechanical ventilation (invasive or non-invasive) prior to day 28, a call to the patient or a doctor/nurse from the rehabilitation health facility is needed to confirm ventilation status on day 28 and their last day of mechanical ventilation.

**Secondary outcomes (secondary endpoints), evaluated up to day 28, include:**

- 1) All-cause death;
- 2) Composite of ICU admission or all-cause death;
- 3) Composite of mechanical ventilation or all-cause death;
- 4) Major bleeding as defined by the ISTH Scientific and Standardization Committee (ISTH-SSC) recommendation (21);
- 5) Red blood cell transfusion ( $\geq 1$  unit);
- 6) Transfusion of platelets, frozen plasma, prothrombin complex concentrate, cryoprecipitate and/or fibrinogen concentrate;
- 7) Renal replacement therapy defined as continuous renal replacement therapy {CRRT} or intermittent hemodialysis {IHD};
- 8) Hospital-free days alive;
- 9) ICU-free days alive;
- 10) Ventilator-free days alive;

- 11) Organ support-free days alive (see Appendix 4 for definition);
- 12) Venous thromboembolism (defined as symptomatic or incidental, suspected or confirmed via diagnostic imaging and/or electrocardiogram where appropriate recognizing that access to diagnostic imaging may be limited in the midst of the COVID-19 pandemic, however confirmatory testing at a later date once exposure risk/personal protective utilization is not an issue is encouraged);
- 13) Arterial thromboembolism (defined as suspected or confirmed via diagnostic imaging and/or electrocardiogram where appropriate recognizing that access to diagnostic imaging may be limited in the midst of the COVID-19 pandemic, however confirmatory testing at a later date once exposure risk/personal protective utilization is not an issue is encouraged);
- 14) Heparin induced thrombocytopenia;
- 15) Trajectories of COVID-19 disease-related biomarkers.

Outcome measures will be obtained from participants' hospital medical records and where applicable through a telephone follow-up, as outlined in Table 5: Study Schedule of Events. The use of BIPAP or CPAP at night or when sleeping for sleep apnea is not considered non-invasive mechanical ventilation or organ support for the purpose of this trial.

#### ***6.4 Duration of the study***

We expect to complete the study in approximately 24 months (for site activation, enrollment, follow-up and close-out), followed by 0.5 months for completion of analyses.

### **7.0 Statistical Plan**

#### ***7.1 Sample Size Calculation***

462 patients (231 per group) are needed to detect a 15% risk difference, from 50% in the control group to 35% in the experimental group (2), with power of 90% at a two-sided alpha of 0.05. No attrition is expected. This calculation takes 2 interim analyses into account. There is no inflation to account for losses to follow-up because we expect these to be very infrequent, and given the nature of the trial, included patients, and outcomes, we may conclude an absence of the primary outcome in patients discharged alive from hospital before 28 days with missing outcome data at day 28.

#### ***7.2 Statistical Analysis***

Primary analyses will be by in the intention-to-treat population of all randomized patients in accordance with the originally allocated intervention. We will conduct a chi-square test for the main analysis of the primary outcome and use a generalized linear regression model with binary distribution and identity link to derive risk difference with 95% confidence intervals. We will conduct subgroup analyses accompanied by tests of interaction for the following variables: age, sex, BMI, time from COVID-19 symptom onset, diabetes mellitus, coronary artery disease, hypertension and race/ethnicity. Logistic regression and linear regression will be used to analyse binary and continuous secondary outcomes after adjustment for age (used for stratification of randomization). Secondary outcomes are exploratory and will not be adjusted for multiple comparisons. A per-protocol analysis of the primary outcome will be restricted to the per-protocol population of participants, defined as those who received experimental or control intervention as allocated during the first 48 hours after randomization. The analysis of safety outcomes will be done in both, the intention-to-treat and per-protocol populations.

If an outcome is missing in more than 5% of the patients, in addition to the pre-planned strategy of assuming non-outcome if patients were discharged alive from hospital before 28 days, a complete case analysis, an inverse probability weighted analysis and multiple imputation on outcome will also be conducted. The statistical analysis plan will be finalized prior to study closure without prior inspection of the data. All analyses will be conducted in Stata version 15.1.

### **7.3 Interim Analysis**

Interim analyses will be done when approximately 25% and 75% of the originally planned number of participants have reached determination of the primary endpoint. A group sequential design has been employed that applies a one-sided boundary. The boundary is based on a Hwang-Shih-DeCani spending function for efficacy. When approximately 75% of the originally planned number of participants have reached determination of the primary endpoint, we will perform a conditional power analysis.

If the conditional power given the accumulated data is <30% and there is robust evidence of harm – either a relevant increase in the risk of major bleeding in the experimental group and the lower limit of the 95% confidence interval for major bleeding excluding 5% on an absolute risk difference scale; or a relevant increase in the risk of all-cause death in the experimental group and the lower limit of the 95% confidence interval for death excluding 1% on an absolute risk difference scale - there will be a non-binding recommendation to stop the trial. If the conditional power is <30%, but there is no robust evidence of harm, we will complete recruitment as planned. The rationale for this approach is that prevention of death (a component of the primary outcome) overrides short-term safety. If major bleeds lead to bleeding related deaths to such an extent that no mortality benefit is likely to be realized the trial should be stopped.

If the conditional power is  $\geq 30$  and  $<60\%$ , we will complete recruitment as planned. If the conditional power is  $\geq 65\%$  and  $<80\%$ , there will be a non-binding recommendation to increase the sample size to achieve 80% power, if deemed feasible from a recruitment perspective. If the conditional power is  $\geq 80\%$ , we will complete recruitment as planned, provided that the interim analysis against the one-sided boundary for efficacy was negative.

Safety reviews will be done by the Data Safety and Monitoring Board at the formal interim analyses mentioned above, and also when approximately 10% and 50% of the originally planned number of participants have reached determination of the primary endpoint. The Data Safety and Monitoring Board can recommend termination or changes to the trial at any time if deemed necessary due to safety concerns. When 10%, 25% and 50% of the originally planned number of participants have reached determination of the primary endpoint, this recommendation will be at the discretion of the Data Safety and Monitoring Board. When approximately 75% of the originally planned number of participants have reached determination of the primary endpoint, the Data Safety and Monitoring Board will be required to also take into account the conditional power when doing the safety review (see above).

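### At the 75% look the pre-specified definition of harm omits the primary composite, so when conditional power is low the written default is to finish recruitment even if the composite is significantly worse

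*Protocol*

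**What the plan says.** Protocol 7.3 plans efficacy analyses at about 25% and 75% of the planned number, with a one-sided Hwang-Shih-DeCani boundary. At 75% a conditional power analysis is added. If conditional power is below 30%, a non-binding recommendation to stop needs robust evidence of harm, which has two alternatives. The first is "either a relevant increase in the risk of major bleeding in the experimental group", with the lower 95% limit of the risk difference above 5 points. The second is the same construction for all-cause death, with the lower limit above 1 point. If neither is met: "If the conditional power is <30%, but there is no robust evidence of harm, we will complete recruitment as planned". The reason given is that preventing death outweighs short-term safety.

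The endpoint that drives conditional power is broader (Protocol 6.3): "The primary composite outcome of ICU admission, non-invasive positive pressure ventilation, invasive mechanical ventilation or death at 28 days". Three of its four components appear in neither harm criterion.

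The same section lets the board recommend termination at any time for safety concerns and leaves the 10%, 25% and 50% reviews to its discretion. At 75%, "the Data Safety and Monitoring Board will be required to also take into account the conditional power when doing the safety review", with a reference back to the rule above. Protocol 10.2 has the board look for an unquestionable difference in effect between arms, develop clinical stopping rules, and notify the steering committee if it finds continuation unacceptable. The SAP contains no harm or futility rule; section 4.2 gives only the final two-sided level of 0.048.

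**The concern.** If therapeutic anticoagulation raised ICU admission or ventilation, the composite would move the wrong way and conditional power would be essentially zero. Unless deaths or bleeds separately cleared their margins, the only written action is to carry on. The stated rationale weighs mortality against bleeding. It gives no reason to continue when the primary outcome itself is worse, so this reads as an omission and not as a deliberate trade-off.

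At stake is the randomization of further patients to an arm already significantly worse on the trial's own endpoint, with no realistic prospect of a positive result. The board would also have pre-specified margins for bleeding and death but none for the composite.

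**Working it through.** **Planned size.** Protocol 7.1 seeks "to detect a 15% risk difference, from 50% in the control group to 35% in the experimental group", "with power of 90% at a two-sided alpha of 0.05", and adds "This calculation takes 2 interim analyses into account" and "No attrition is expected". With pooled variance and mean risk 0.425:

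n = [1.960·√(2·0.425·0.575) + 1.2816·√(0.50·0.50 + 0.35·0.65)]² / 0.15² = 226.2, so 227 per arm (454).

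A Hwang-Shih-DeCani boundary with gamma = −4 (assumed; the documents do not state gamma) inflates this by 1.017 to 231 per arm, the stated 462. The choice of gamma does not affect what follows.

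**75% look.** 0.75 × 462 = 346.5, about 173 per arm.

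**What each criterion needs.** Wald lower limit: L = d − 1.96·√[(p₁(1−p₁) + p₀(1−p₀))/173].

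| Outcome | Control | Smallest experimental count | d (points) | L (points) | Threshold |
|---|---|---|---|---|---|
| Composite | 86 (50%) | 105 | 11.0 | 0.6 | 0 (proposed) |
| Death | 14 (8%) | 28 | 8.1 | 1.3 | 1 |
| Major bleeding | 3 (2%) | 21 | 10.4 | 5.2 | 5 |

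One event fewer in the experimental arm fails in each row (104, 27 and 20).

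**Conditional power at that composite result.** With z = −2.05 in the efficacy direction, t = 0.75 and final critical value 1.977 (two-sided 0.048):

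CP = 1 − Φ{[1.977 − z√t − θ(1−t)]/√(1−t)}.

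- Current trend, θ = z/√t = −2.37: the argument is (1.977 + 1.779 + 0.593)/0.5 = 8.70, so CP is effectively 0.
- Design effect, θ = 1.960 + 1.282 = 3.24: the argument is (1.977 + 1.779 − 0.810)/0.5 = 5.89, so CP is about 2 × 10⁻⁹.

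The branch for conditional power below 30% therefore always applies.

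**How often the rule says continue.** Simulation of 400,000 trials per row at 173 per arm. The true composite is 50% control against 65% experimental, the planned effect reversed. Deaths are nested in the composite and major bleeds are 2% against 3%. The composite is significantly worse in about 82% of trials in every row.

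| Deaths, control vs experimental | Neither harm criterion met, among significantly worse trials |
|---|---|
| 8% vs 10% | 94% |
| 20% vs 26% | 77% |
| 32.8% vs 42.6% | 53% |
| 40% vs 52% | 34% |

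The documents give no planning rates for death or bleeding, so all these rates are assumptions. The last two control death rates are the 28-day mortalities of heparin users in the retrospective cohort described in Protocol 1.0, the source that 7.1 also cites for its planning rates. In the last three rows deaths rise in the same proportion as the composite (×1.3). With deaths 8% vs 12% and bleeds 2% vs 5%, the share is 83%.

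**Exposure.** 231 − 173 = 58 further experimental patients at most, and 58 × 0.15 ≈ 9 extra composite events at +15 points. The look waits for 28-day outcomes. At the planned average pace (462 over 685 days), about 28 × 462/685 ≈ 19 patients across both arms would already have been randomized.

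**Cost of a composite criterion.** With 50% in both arms, the lower limit exceeds 0 in about 2.4% of trials, all with conditional power near zero.

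**The case against.** The strongest reply is that the rule is a default inside a wider framework. The board may recommend termination at any time for safety concerns. Protocol 10.2 has it develop stopping rules and look for an unquestionable difference in effect, with no direction specified. Having to consider conditional power adds information and does not forbid stopping. Reviews at 10%, 25% and 50% come first: in the +15-point scenario the composite is already nominally worse in about 65% of trials at the 50% review (about 115 per arm). The rule also has a stated mortality-first rationale, and ICU admission is a clinician's decision in an open-label trial without an events committee, which is a reason for caution with a nominal threshold.

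Much of this stands, and it rules out several stronger readings a reader might infer:

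- That the plan obliges the trial to continue: the board's powers contradict this.
- That no rule anywhere covers a harmful composite: the board's terms of reference are not among the documents, so this can be said only of the Protocol and SAP.
- That the bleeding and death criteria can never stand in for the composite: at 40% vs 52% deaths one of them is met in about 66% of the significantly worse trials.
- That the whole last quarter would be exposed: some of those patients would already have been randomized by the time of the look.

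The objection does not supply a criterion. Neither passage on the board's powers says whether an excess of ICU admission or ventilation is a safety concern, or how large a difference is unquestionable. At 75% the text refers the board back to a rule whose only instruction for this case is to continue.

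**Conclusion.** The gap is a missing pre-specified criterion at the 75% look, together with three statements (the 7.3 rule, the board's discretion in 7.3, and its role in 10.2) that are not reconciled. Under a true 50% vs 65% composite, the written rule says continue in roughly 34% to 94% of the significantly worse trials. The share depends mainly on assumed mortality, so no single figure from that range should be quoted alone. These shares describe the rule before any board discretion, and 58 experimental patients is an upper limit. The point merits a change because it concerns participant protection and is cheap to close, but it is not evidence that the board would be unable to act.

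**What to change.** In Protocol 7.3, add a third, non-binding criterion for robust evidence of harm: an increase in the primary composite in the experimental group with the lower limit of the 95% confidence interval of the risk difference (experimental minus control) above 0. The board should also weigh the direction of all-cause death, in keeping with the mortality-first rationale. State that the criterion operates alongside the board's powers in 7.3 and 10.2, and carry the same wording into the board's terms of reference.

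The cost is a sentence or two in each document. There is no efficacy alpha cost, because the criterion can only lead to stopping for harm. It would be met in about 2.4% of trials with no true effect, all with almost no chance of a positive result. Because ICU admission involves clinician judgement in an open-label trial, the recommendation should stay non-binding.
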